APPENDIX 11: Poly-ICLC Ophthalmology Worksheet

PID1/PID2	NF111-	Date of Visit:
-----------	--------	----------------

Best Corrected Teller Grating Acuity measured at 55cm (Cycles/cm, choose best card achieved):

Right Eye:

- 38
- 26
- 19
- 13
- 9.8
- 6.5
- 4.8
- 3.2
- 2.4
- 1.6
- 1.3
- 0.86
- 0.64
- 0.43
- 0.32
- 0.23 Low vision/HM/LP
- 0.16 No light perception
- Not Done (please select the reason):
 - Test not attempted
 - Subject unable to cooperate
 - Unevaluable Eye / Other

Please specify: _____

Left Eye:

- 38
- 26
- 19
- 13
- 9.8
- 6.5
- 4.8
- 3.2
- 2.4
- 1.6
- 1.3
- 0.86
- 0.64
- 0.43
- 0.32
- 0.23 Low vision/HM/LP
- 0.16 No light perception
- Not Done (please select the reason):
 - Test not attempted
 - Subject unable to cooperate
 - Unevaluable Eye / Other

Please specify: _____

Best Corrected HOTV Visual Acuity using ATS protocol (in logMAR):

Right Eye:

- 0.1
- 0.0
- 0.1
- 0.2
- 0.3
- 0.4
- 0.5
- 0.6
- 0.7
- 0.8
- 0.9
- 1.0
- 1.1
- 1.2
- 1.3
- 1.4
- 1.5
- 1.6
- 1.7(>20/800, hand motions or light perception)
- 1.8(No Light Perception)
- Not Done (please select the reason):
 - Test not attempted
 - Subject unable to cooperate
 - Unevaluable Eye / Other

Please specify: _____

Left Eye:

- 0.1
- 0.0
- 0.1
- 0.2
- 0.3
- 0.4
- 0.5
- 0.6
- 0.7
- 0.8
- 0.9
- 1.0
- 1.1
- 1.2
- 1.3
- 1.4
- 1.5
- 1.6
- 1.7(>20/800, hand motions or light perception)
- 1.8(No Light Perception)
- Not Done (please select the reason):
 - Test not attempted
 - Subject unable to cooperate
 - Unevaluable Eye / Other

Please specify: _____

Visual Field by Confrontation Method (number of abnormal quadrants per eye):

Right Eye:

- 0 - normal visual field
- 1 - abnormal quadrant
- 2 - abnormal quadrants
- 3 - abnormal quadrants
- 4 - abnormal quadrants
- Not Done (please select the reason):
 - Test not attempted
 - Subject unable to cooperate
 - Unevaluable Eye / Other

Please specify: _____

Left Eye:

- 0 - normal visual field
- 1 - abnormal quadrant
- 2 - abnormal quadrants
- 3 - abnormal quadrants
- 4 - abnormal quadrants
- Not Done (please select the reason):
 - Test not attempted
 - Subject unable to cooperate
 - Unevaluable Eye / Other

Please specify: _____

Optic Nerve Swelling:

Right Eye:

- Swelling
- Normal
- Did not perform

Left Eye:

- Swelling
- Normal
- Did not perform

Optic Pallor:

Right Eye:

- Pallor
- Normal
- Did not perform

Left Eye:

- Pallor
- Normal
- Did not perform

In the ophthalmologist's opinion has overall visual acuity declined since last visit?

Right Eye:

- Yes, Due to:
 - Optic Pathway Glioma
 - Amblyopia
 - Unsure (OPG and/or suspected amblyopia)
 - Other
- Please specify: _____
- No
- N/A - Baseline

Left Eye:

- Yes, Due to:
 - Optic Pathway Glioma
 - Amblyopia
 - Unsure (OPG and/or suspected amblyopia)
 - Other
- Please specify: _____
- No
- N/A - Baseline

In ophthalmologist's opinion is the overall visual acuity NORMAL?

Right Eye:

- Yes
- No, Due to:
 - Optic Pathway Glioma
 - Amblyopia
 - Unsure (OPG and/or suspected amblyopia)
 - Other
- Please specify: _____

Left Eye:

- Yes
- No, Due to:
 - Optic Pathway Glioma
 - Amblyopia
 - Unsure (OPG and/or suspected amblyopia)
 - Other
- Please specify: _____

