9.1. Visual Acuity (best corrected)

IMPORTANT NOTE: if the VA data at a particular visit is felt to be unreliable due to poor cooperation, testing should be repeated within 4 weeks. Only the visit believed to have yielded the most reliable data should be reported.

Teller acuity testing using TAC II cards will be attempted on all participants at all visits. All VA testing will be performed by study personnel who have undergone TAC teaching by the study team. VA testing will be performed in each eye separately at a distance of 55 cm in all participants. The tester will utilize the “Two down, one up” protocol to achieve the best visual acuity. Acuity will be reported in cycles/cm by the site and converted by the operations center to logMAR. Reasons for VA testing not being completed will be recorded.

Table 8: Visual acuity in feet and logMAR equivalents for acuity in cycles/cm

Card @ 55 cm (Cycles/cm)	VA equivalent	logMAR
26	20/24	0.06
19	20/32	0.20
13	20/47	0.36
9.8	20/63	0.49

6.5	20/94	0.66
4.8	20/130	0.80
3.2	20/190	0.97
2.4	20/260	1.10
1.6	20/380	1.27
1.3	20/470	1.36
0.86	20/710	1.54
0.64	20/960	1.67
0.43	20/1400	1.84
0.32	20/1900	1.97

HOTV will be attempted on participants who are old enough. HOTV will be performed using the PEDIG ATS-HOTV computerized protocol in each eye separately at a recommended testing distance of 3 meters in all participants. Acuity will be reported in logMAR. Reasons for VA testing not being completed will be recorded.

For primary analysis, the VA endpoint will be the difference between best-corrected VA at baseline and at approximately 1 year (i.e., at the post-cycle 12 assessment).

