9.5. Visual Response

Primary functional outcome is based on visual acuity (VA) and is defined as the difference in VA after approximately 12 cycles of treatment. Eyes above the visual “ceiling” (0.2 logMAR below normal for age or 0.2 logMAR below a previous reliably documented VA) at baseline cannot improve and will be excluded from the analysis of visual response. A significant improvement in VA will be defined as a decrease of ≥ 0.2 logMAR (corrected for age) from baseline (pre-treatment baseline) to end of ~12 cycles of treatment. The analysis will be based on per participant outcome (rather than per eye).

A significant improvement in VA will be defined as a decrease of ≥ 0.2 logMAR from baseline (pre-treatment baseline) to end of ~12 cycles of treatment.

Ophthalmologic (Visual Acuity) Response Criteria

- Visual Responsive ≥ 0.2 logMAR improvement in VA compared to baseline
- Stable VA = does not meet criteria for Improved or Worsening VA compared to baseline
- Visual Progressive Disease ≥ 0.2 logMAR worsening compared to baseline*

* 0.2 logMAR worsening (or up to a 2-card drop in Teller Acuity) will not be considered visual progressive disease at the first on-therapy staging evaluation (at 12 weeks), if the tumor is stable or smaller on MRI. In these cases, a repeat visual acuity assessment will be required 6-12 weeks later to confirm that further visual progression is not occurring. If the repeat visual acuity is stable or improved (0.2 logMAR or less [or a 2 card drop in Teller Acuity or less] from pre-treatment baseline), the patient will remain on protocol therapy. If the visual acuity is now > 0.2 logMAR (or > 2 card drop in Teller acuity) worse from pre-treatment confirmed by a second exam, then the participant will be removed from the protocol.

Visual worsening ≥ 0.2 logMAR in the setting of possible pseudoprogression should be discussed on a case-by-case basis with the study chair. In most cases, patient may continue on study until pseudoprogression vs progression is confirmed. Corticosteroids may be considered, and a short interval repeat eye exam is recommended. If a repeat vision exam shows continued deterioration of visual function, then patient will be permanently removed from therapy and the time of progression will be the date of the initial MRI or vision exam showing progression. See section 10.4 for additional information regarding possible pseudoprogression.

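### An eye already at the low-vision/light-perception code at baseline that loses all light perception is classed as stable, and the two acuity charts' floor codes contradict each other

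*Combined protocol and SAP*

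**What the plan says.** Section 9.5 has three visual classes, all relative to baseline. Response is "0.2 logMAR improvement in VA compared to baseline" of at least that size; progression is "Visual Progressive Disease ≥ 0.2 logMAR worsening compared to baseline"; Stable VA is whatever "does not meet criteria for Improved or Worsening VA compared to baseline". At the first on-therapy evaluation (12 weeks), a 0.2 logMAR or up to two-card Teller drop is not counted as progression if the tumor is stable or smaller, and a repeat examination is required. Eyes above a visual ceiling are excluded from the response analysis. Nothing is said about eyes at the floor.

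Appendix 11 gives the codes below the last measurable step. On HOTV these are "1.7(>20/800, hand motions or light perception" and "1.8(No Light Perception". On Teller they are 0.23 cycles/cm, labelled low vision/HM/LP (HM/LP meaning hand motions or light perception), and "0.16 No light perception".

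For Teller, Section 9.1 states: "Acuity will be reported in cycles/cm by the site and converted by the operations center to logMAR". Table 8 supplies the conversion for 14 cards, from 26 cycles/cm (0.06) to 0.32 cycles/cm (1.97). The worksheet also lists 38, 0.23 and 0.16, which have no row. Teller is attempted at every visit, and HOTV once the child is old enough. The endpoint compares baseline with the assessment after cycle 12, without naming the chart.

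The Protocol Summary and Section 1 list visual outcome as exploratory, while Section 14 places visual acuity under secondary endpoints. Section 10.4 refers to Section 9.5 for visual progressive disease.

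**The concern.** Loss of the last light perception is a change of state, but a purely numeric rule sees only the distance between two arbitrary codes. If that distance is under 0.2, the rule reports no change. If the two charts give the same state different numbers, a comparison across charts can report a change where there was none, or a change in the wrong direction.

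Optic pathway patients may enter because their vision has worsened (Section 3.1), so some may have eyes near the floor. At most 20 participants will be enrolled and only those with optic pathway tumors contribute, so one misclassified participant would be visible in the result.

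**Working it through.** **Inputs.** The 0.2 threshold and the classes are from Section 9.5, the off-chart codes from Appendix 11, and the Teller conversion from Table 8 in Section 9.1.

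**Reproducing the plan's conversion.** The formula logMAR = log10(30 / cycles per cm) returns all 14 rows of Table 8 to two decimals. For example, log10(30/26) = 0.062, log10(30/0.43) = 1.844 and log10(30/0.32) = 1.972. It also returns the six distinct Teller values in Table 9 to three decimals. Exact geometry at 55 cm adds about 0.018 to every value. That does not match Table 8, and it leaves differences within Teller unchanged.

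**Extending it to the worksheet codes without a row.**
- 0.23 cycles/cm: log10(30/0.23) = 2.115
- 0.16 cycles/cm: log10(30/0.16) = 2.273

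**Same chart, ending at no light perception (NLP).**

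| Baseline | Follow-up | Change | Class under the 9.5 list |
|---|---|---|---|
| HOTV 1.7 | HOTV 1.8 | 1.8 − 1.7 = +0.10 | Stable VA |
| HOTV 1.6 | HOTV 1.8 | 1.8 − 1.6 = +0.20 | Visual Progressive Disease |
| HOTV 1.5 | HOTV 1.8 | 1.8 − 1.5 = +0.30 | Visual Progressive Disease |
| Teller 0.23 | Teller 0.16 | log10(0.23/0.16) = +0.158 | Stable VA |
| Teller 0.32 | Teller 0.16 | log10(0.32/0.16) = +0.301 | Visual Progressive Disease |

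Only eyes that start at the low-vision/HM/LP code are missed. The HOTV 1.6 to 1.8 case sits exactly on the threshold and evaluates as below 0.2 in floating-point code unless the difference is rounded first. At the 12-week evaluation with a stable or smaller tumor, both HOTV 1.6 to 1.8 (0.2) and Teller 0.32 to 0.16 (two cards) fall inside the tolerance. The second case is two cards but 0.301 logMAR, so the two limbs of that tolerance do not describe the same change.

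**Different charts.** HOTV gives NLP the value 1.8. Table 8 gives the measurable Teller acuities 0.43 and 0.32 cycles/cm the worse values 1.84 and 1.97.

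| Baseline | Follow-up | Change | Class |
|---|---|---|---|
| Teller 0.23 (low vision/HM/LP) | HOTV 1.8 (NLP) | 1.8 − 2.115 = −0.315 | Visual Responsive |
| Teller 0.16 (NLP) | HOTV 1.8 (NLP) | 1.8 − 2.273 = −0.473 | Visual Responsive, state unchanged |
| Teller 0.32 | HOTV 1.8 (NLP) | 1.8 − 1.972 = −0.172 | Stable VA |
| HOTV 1.8 (NLP) | Teller 0.16 (NLP) | 2.273 − 1.8 = +0.473 | Visual Progressive Disease, state unchanged |

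With exact geometry the first figure is −0.333, and the class is the same.

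**The case against.** - **Blindness in general.** A reader might infer that any eye that goes blind is called stable. The documents do not support that. The comparison is with baseline, and loss from HOTV 1.6 or better, or Teller 0.32 or better, reaches 0.2. This limits the point to eyes already at the low-vision/HM/LP code.
- **Small steps at the bottom.** A reader might also take the sub-0.2 floor steps (0.10 to 0.158) as a special defect. They are not. All 13 steps within Table 8 are 0.09 to 0.18 and HOTV steps are 0.1, so a single-step change is stable everywhere by design. What is particular to the floor is that the last step is a loss of light perception and no larger numeric drop is available to that eye.
- **The codes are broad.** HOTV 1.7 includes anything worse than 20/800, and Teller 0.23 includes low vision. A move from the last measurable value into these codes may be one line or one card. Counting it automatically as worsening could create false events, so that step should stay under the 0.2 rule.
- **Mixed charts.** Teller is attempted at every visit, the worksheet has separate fields for the two tests, and nothing directs a mixed comparison. A reader should not infer that one will be made. It remains true that nothing bars it, that the endpoint chart is unnamed, and that a child can become able to do HOTV during the study.
- **Other information is collected.** The worksheet records NLP, field quadrants and the ophthalmologist's view of decline, and Section 3.5 lists clinical progression and physician judgement as grounds for stopping therapy. The loss is therefore on record, but the Section 9.5 classification uses none of these items.

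**Conclusion.** The point holds in a narrow form. An eye at HOTV 1.7 or Teller 0.23 at baseline that goes to no light perception changes by 0.10 or 0.158 logMAR and is Stable VA under Section 9.5, which is a wrong result under the rule as written. Separately, the charts' floor codes conflict, so a Teller 0.23 baseline read against HOTV 1.8 scores as a 0.315 improvement.

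Assumptions:
- The 0.158 step holds for any log10 conversion. The 2.115 and 0.315 figures extend Table 8's formula to a card without a row, and the operations center could assign another value.
- No age correction is applied. One sentence in Section 9.5 mentions one, but its near-duplicate and the criteria list do not. Using the Table 9 norms could change the class in young children; the correction is zero from age 6.
- The result is per eye. The analysis is per participant, and how two eyes are combined is not stated.
- The number of eyes at the floor is not given and may be zero.

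The primary endpoint is tumor response, and its size criteria are unaffected.

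**What to change.** For the visual outcome analysis only, in Section 9.5 and Appendix 11:

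1. Count a move from the low-vision/HM/LP code to no light perception as worsening, and the reverse as improvement, whatever the numeric difference. Leave the step from the last measurable value to the low-vision/HM/LP code under the 0.2 rule.
2. Compute each eye's change within one test done at both baseline and the post-cycle assessment: HOTV if done at both, otherwise Teller. Round the difference before comparing it with 0.2.
3. Add logMAR values for cards 38, 0.23 and 0.16 to Table 8. The formula behind the table gives log10(30/38) = −0.10, 2.12 and 2.27.

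The sponsor must also reconcile Section 9.5 (visual progressive disease, the two-card tolerance and the removal wording) with Table 8 and Appendix 11. No removal rule is proposed here.

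The cost is wording in the analysis plan and worksheet. Every entry needed is already collected. A few eyes without a common test at both visits would drop out of the change analysis.
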